- A. The post-intervention HbA1c levels in the intervention group will be compared to the control group using linear regression model after adjusting for baseline HbA1c levels. Additionally, average percentage change in HbA1c level across the 2 groups will be computed and compared using 2 sample t-test or Wilcoxon rank sum test (depending on the distribution of data).
- B. **Outcome:** The post-intervention HbA1c levels in the intervention group will be compared to the control group using linear regression model after adjusting for baseline HbA1c levels. Additionally average percentage change in HbA1c level across the 2 groups will be computed and compared using 2 sample t-test or Wilcoxon rank sum test (depending on the distribution of data). The secondary outcomes of interest are additional clinical measures (blood pressure, LDL, HDL), dietary habits, diabetes self-management behaviors, Diabetes and CVD knowledge, and problem-solving skills for health-related problems as assessed by instruments listed in Table 5.
- C. **Study results to participants:** We will make available any published study results. Our study team will also make available any community presentations to allow participants to learn about the final findings of the study and next steps.
- D. **Publication Plan:** We will publish study results to peer-reviewed journals: preliminary findings and a protocol paper. All identifying information will be removed before publication.

VI. Bibliography / References / Literature Cited: see attachment

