Primary Hypothesis: Participants randomized to eDECIDE (intervention group) will have comparable improvement in HbA1c compared to those randomized to traditional DECIDE (control group) at the end of 18-weeks.

Secondary Hypothesis: Participants randomized to eDECIDE (intervention group) will have comparable improvement in problem-solving skills, diabetes self-management knowledge and behaviors, and clinical measures compared to traditional DECIDE (control group) at the end of 18-weeks.

B. Background and Significance

1. **Study Significance:** This web-based approach will allow for future studies (using mHealth mobile applications) that can examine best practices for which type of problem-solving skills training is most effective to improve diabetes health outcomes for individuals. Results will inform the development of interventions aimed at reducing complications from uncontrolled diabetes as well as interventions aimed at promoting problem-solving and self-management. Identifying how to make problem-solving interventions more accessible would strengthen current investigations into improving health outcomes among underserved populations. It is believed that the minimal risk involved in the proposed study is reasonable considering that it could lead to more effective ways to manage diabetes among vulnerable. Since participation in traditional diabetes self-management programs is low, delivering tailored problem-solving skills training could increase self-efficacy and adherence among *African Americans*, thus improving glycemic control and further reducing health complications.

We propose to design and test a web-based application of the DECIDE curriculum for African Americans with uncontrolled diabetes. According to a Pew Internet study, 62% of African Americans have home access to the Internet,²⁷ and a previous web-based intervention indicated 80% of urban African Americans living with diabetes were using computers.²⁸ This application is not only a feasible approach to skills training, but innovative and cost-effective, allowing more flexibility, control, and self-directed access to training than face-to-face group sessions do. This new modality to deliver problem-solving interventions has the potential to reach much more of the African American population by providing easier access to diabetes self-management education.

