C. Sample size, statistical methods, and power calculation

The primary outcome of interest is HbA1c measurement in the traditional DECIDE (control) group and eDECIDE (intervention) group. A .5% change in HbA1c has been considered clinically meaningful. The standard deviation in both arms is assumed to be 1.3%.⁶¹ Based on 2 sample t-test, assuming type I error rate of 5%, and attrition rate of 20%, with 35 participants in each group, the study is powered at 80% to detect a change in HbA1c level of at least 1% between the 2 groups. Hill-Briggs' intervention was successful in detecting HbA1c change of at least 1% in a previous study. We will recruit 100 participants allowing for attrition to reach our goal of 70 for the pilot RCT. Block randomization with block size of 10 will be employed. Within each block 5 participants will be assigned at random to control and 5 to intervention group using computer derived labels.

For baseline characteristics of data, descriptive statistics will be reported as mean and standard deviation for continuous variables, and as count and percentage for categorical variables. Depending on the distribution of the continuous variables Wilcoxon rank sum test or t-test will be used to test for difference in continuous variables across the control and intervention group. Chi-Square test of independence will be used to assess the association between categorical variables and the two groups. The analysis will be based on "Intention-to-treat" principle. A 2-sided p-value of 0.05 will be used to assess statistical significance. Missing Data: If the proportion of missing data is small (5%), complete case analysis will be carried out. If the proportion is higher, then multiple imputations will be used to impute missing values.

The post-intervention HbA1c levels in the intervention group will be compared to the control group using linear regression model after adjusting for baseline HbA1c levels. Additionally, average percentage change in HbA1c level across the 2 groups will be computed and compared using 2 sample t-test or Wilcoxon rank sum test (depending on the distribution of data).

The secondary outcomes of interest are additional clinical measures (blood pressure, LDL, HDL), dietary habits, diabetes self-management behaviors, Diabetes and CVD knowledge, and problem-solving skills for health-related problems as assessed by instruments listed in Table 5.

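### The hypotheses claim comparability, but the plan only tests for a difference and gives no margin or confidence-interval rule by which comparability could be concluded

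*Combined protocol and SAP*

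**What the plan says.** Section I.A (Aim and Hypotheses) puts the primary hypothesis as follows: "Participants randomized to eDECIDE (intervention group) will have comparable improvement in HbA1c compared to those randomized to traditional DECIDE (control group"), at 18 weeks. The secondary hypothesis says that eDECIDE participants "will have comparable improvement in problem-solving skills, diabetes self-management knowledge and behaviors, and clinical measures compared to traditional DECIDE (control group"), again at 18 weeks. Section I.C describes the control programme, DECIDE, as already proven in community settings.

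The statistical text appears in II.C and again in V. For the primary outcome, post-intervention HbA1c in the intervention group "will be compared to the control group using linear regression model after adjusting for baseline HbA1c levels". Percentage change is also compared by t-test or Wilcoxon test. The only criterion is: "A 2-sided p-value of 0.05 will be used to assess statistical significance". The analysis follows intention-to-treat.

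The sample size in II.C, repeated under Subject Enrollment, uses a two-sample t-test with SD 1.3, "assuming type I error rate of 5%, and attrition rate of 20%, with 35 participants in" each group, and concludes that "the study is powered at 80% to detect a change in HbA1c level of at least 1% between the 2 groups". The same paragraph says: "A .5% change in HbA1c has been considered clinically meaningful". That 0.5 figure is used neither as the design difference nor as a margin. The plan names no margin, equivalence or non-inferiority test, confidence-interval criterion or per-protocol analysis.

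**The concern.** The control is an active programme, so the question is whether web delivery keeps its benefit. A test of no difference does not answer that. A significant result would either contradict the hypothesis or show eDECIDE to be better. A non-significant result shows only that the data did not rule out zero, and at this sample size that is compatible with a loss that the plan calls clinically meaningful. Neither outcome of the planned test supports the word comparable.

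What is at stake is the headline conclusion on HbA1c, and the same statement for each secondary outcome. With no rule fixed in advance, what counts as comparable would be settled after the results are known.

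**Working it through.** **Inputs from II.C.** SD 1.3 in both arms; two-sided alpha 0.05; 1:1 allocation; 35 per group; attrition 20%; 100 recruited to reach 70; meaningful change 0.5 points; design difference 1 point.

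**Analysed numbers per arm considered.** 28 (35 × 0.8); 35 (70 analysed); 40 (100 × 0.8 / 2); 50 (all 100 recruits, no loss). The text does not make clear whether 35 is before or after attrition, so the range covers both readings.

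**1. The plan's own figure.** By the exact non-central t calculation, a 1-point difference with SD 1.3 has power 79.2% at 27 per arm and 80.7% at 28. So 28 per arm are needed, and 28/0.8 = 35. The stated size reproduces. It is a calculation for detecting a difference.

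**2. How often the planned test misses a true 0.5-point deficit.** SE = SD × √(2/n); half-width of the 95% CI = t(0.975, 2n−2) × SE, which is also the smallest observed difference that reaches p<0.05; P(p>0.05) comes from the non-central t with non-centrality 0.5/SE. For n = 35: SE = 1.3 × √(2/35) = 0.311; half-width = 1.9955 × 0.311 = 0.62; non-centrality = 0.5/0.311 = 1.61; P(p>0.05) = 0.645 to 0.646, i.e. 65%.

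| Analysed per arm | SE | 95% CI half-width | P(p>0.05), true deficit 0.5 |
|---|---|---|---|
| 28 | 0.347 | 0.70 | 71% |
| 35 | 0.311 | 0.62 | 65% |
| 40 | 0.291 | 0.58 | 60% |
| 50 | 0.260 | 0.52 | 52% |

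The unadjusted half-width exceeds 0.5 in every row.

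**3. Allowing for baseline adjustment.** The plan gives no baseline/post correlation r, so r is an assumption. If 1.3 is the SD of the 18-week level, the residual SD is 1.3 × √(1−r²): 1.126 at r = 0.5 and 0.928 at r = 0.7. Repeating step 2 with 2n−2 degrees of freedom as an approximation:

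| Analysed per arm | P(p>0.05), r = 0.5 | P(p>0.05), r = 0.7 |
|---|---|---|
| 28 | 63% | 49% |
| 35 | 55% | 40% |
| 40 | 50% | 34% |

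**4. What a non-inferiority rule would deliver at the planned size.** Take 0.5 points as a candidate margin and a true difference of 0. Power is the chance that the upper 95% limit falls below 0.5, from the same non-central t.

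| Analysed per arm | Unadjusted | r = 0.7 |
|---|---|---|
| 28 | 29% | 51% |
| 35 | 35% | 60% |
| 50 | 48% | 76% |

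For 80% power without adjustment, n = 2 × (1.3 × (1.960 + 0.842)/0.5)² = 106.1, so 107 per arm evaluable. With 20% attrition this is 107/0.8 = 133.75, so 134 per arm or 268 in total. The answer depends heavily on the margin: 295 per arm evaluable at 0.3 points, 166 at 0.4, 27 at 1.0.

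**The case against.** Four objections have force.

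- **A reader might infer that the investigators will treat p>0.05 as proof of comparability.** The documents do not say so. The p-value sentence is generic and follows the baseline comparisons. What can be said is that the plan does not state how comparability would be concluded and offers no other criterion.
- **A reader might infer that the trial cannot inform its question at all.** That goes too far. The baseline-adjusted regression yields the difference and its standard error, hence an interval. What is missing is a rule for interpreting it.
- **It is a pilot.** Section II.A gives a feasibility goal, and that argues against requiring a fully powered non-inferiority trial. It does not remove the mismatch: HbA1c is the named primary outcome with a formal power calculation, and II.D states an intent to determine efficacy.
- **A reader might infer that poor adherence under intention-to-treat always pushes towards comparability.** That holds if adherence falls similarly in both arms. If it falls mainly with eDECIDE, the gap widens. The documents give no basis for assuming either.

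It is also fair that 0.5 points is called a meaningful change, not an acceptable loss between arms, so it cannot simply be adopted as the margin. The sample-size arithmetic is correct for the test that it describes.

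**Conclusion.** The point stands as a mismatch between hypothesis and analysis, and it needs correcting before results are seen. The primary and secondary hypotheses assert comparability; the analysis and sample size address a difference; nothing links the two. A non-significant result must not be taken as comparability, because a true 0.5-point deficit would go undetected in 60% to 71% of trials with 28 to 40 per arm, or 34% to 49% if adjustment achieves a correlation of 0.7. These figures rest on the plan's SD of 1.3, equal arms and normal-theory tests; the correlation is assumed. The conclusion holds whether 35 per group is read as before or after attrition.

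**What to change.** **Recommended at the planned size.** Keep the baseline-adjusted regression. Restate the primary and secondary hypotheses as estimation: for HbA1c, the adjusted 18-week difference (eDECIDE minus DECIDE) with a two-sided 95% CI; for each secondary outcome, the corresponding difference with its CI. Add a sentence that p>0.05 will not be taken as evidence of comparability.

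**If the sponsor wants to keep a comparability claim.** Pre-specify and justify a non-inferiority margin before results are seen; 0.5 points is a candidate only. Claim comparability on HbA1c only if the upper 95% limit lies below the margin. Disclose the power at the planned size (at 0.5 points with 28 to 35 per arm, about 29% to 35% unadjusted and 51% to 60% at an assumed correlation of 0.7), or re-size.

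Any analysis of completers should be supportive only: it is not a randomised comparison, and the direction of bias from non-adherence depends on whether it differs by arm.

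**Cost.** The estimation route changes wording only; data, visits and model stay the same. The downside is that the trial will probably report an interval, or an inconclusive result, and not that the programmes are comparable. The non-inferiority route at adequate power would need many more participants unless the margin is wide.

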1. **Blinding Procedures:** This study will not involve blinding (masking). Participants and research staff will be aware of random group assignment.
2. **Subject Enrollment:** The primary outcome of interest is HbA1c measurement in the traditional DECIDE (control) group and eDECIDE (intervention) group. A .5% change in HbA1c has been considered clinically meaningful. The standard deviation in both arms is assumed to be 1.3%.⁶¹ Based on 2 sample t-test, assuming type I error rate of 5%, and attrition rate of 20%, with 35 participants in

each group, the study is powered at 80% to detect a change in HbA1c level of at least 1% between the 2 groups.²⁴⁻²⁵ Hill-Briggs' intervention was successful in detecting HbA1c change of at least 1% in a previous study.²⁴⁻²⁵ We will recruit 100 participants allowing for attrition to reach our goal of 70 for the pilot RCT. Block randomization with block size of 10 will be employed. Within each block 5 participants will be assigned at random to control and 5 to intervention group using computer derived labels.

D. Subject Criteria (See Vulnerable Populations appendix, if applicable): While uncontrolled diabetes affects more than one racial/ethnic group, our study will focus on African American adults because the burden of disease and consequent health complications is greatest among this population, particularly in the state of Kansas. Here, African Americans have the highest diabetes prevalence (15.7%) compared to 8.7% for non-Hispanic whites. In Sedgwick County (the county in which KUSM-W is located), African Americans make up 9% of the population, but have the highest prevalence of diagnosed diabetes within the county at 15%, with Non-Hispanic whites at 8.1%.⁵⁴ This study will take place in our local community where improvements and innovations in access to diabetes self-management services are greatly needed. Examining multiple racial/ethnic groups is beyond the scope of the current application. Our intent is to determine the efficacy of eDECIDE with a focus on our most at-risk group (i.e., African Americans). Future studies will allow the resources and time to expand the study population beyond African Americans.

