1. Inclusion criteria: Potential participants will be initially screened based on clinic (KU Internal Medicine Clinic) databases. They will be included if they have an HbA1c of > 7%, absence of significant comorbidities that limit adherence to self-management protocol, or expected to limit lifespan to < 3 years (chest pain, amputation, cancer diagnosis) based on medical chart audit review, are deemed suitable by clinicians, are African American, and are at least 21 years and older. The candidate will contact those who meet inclusion criteria to further undergo a telephone eligibility screen. The screen will ascertain eligibility based on no current participation in a self-management program and daily access to the Internet (in a home or private location).
2. Exclusion criteria: During the baseline visit, potential participants will then be screened for exclusion criteria: visual and cognitive impairment,⁵¹⁻⁵² inability to give informed consent, and unable to complete baseline assessment (clinical measures, study questionnaires, venipuncture).
3. Withdrawal/Termination criteria: Subject's participation will be terminated if requested by the subject. Subject's will need to continue to meet eligibility requirements to remain in the study (i.e. Internet access, etc.) to remain in the study.
4. A study subject can't participant in another study that is related to diabetes self-management as this may compromise out study outcomes.

E. Specific methods and techniques used throughout the study

1. **Laboratory tests:** Our study will collect and possibly perform blood draws (approximately 2 tablespoons)- to measure HbA1c and Cholesterol level. This blood draw would be collected at baseline, post-intervention (18 weeks) and again at 3-month follow-up. The laboratory test would be conducted either by the participating clinic or a contracted laboratory for participants to visit.

Behavioral questionnaires: Health-problem-solving survey, Diabetes self-care survey,

patient-provider communication survey

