 - a. Delivering a problem-solving intervention through a web-based component is an innovative way to reach the desired underserved population which is the focus of this application. This approach will allow for greater resources and tools at the disposal of subjects involved in the study, thus improving their self-management and health outcomes related to their disease.

- b. In addition, the web-based format allows subjects to receive tailored real-time feedback on potential problem-solving issues that emerge (i.e. dietary and physical activity issues, other self-care issues), on diabetes self-management knowledge.
- c. This approach (web-based) will allow for future studies (using mHealth mobile applications) that can examine best practices for which type of problem-solving skills training is most effective to improve diabetes health outcomes for particular individuals. Results will inform the development of interventions aimed at reducing complications from uncontrolled diabetes as well as interventions aimed at promoting problem-solving and self-management. Identifying how to make problem-solving interventions more accessible would strengthen current investigations into improving health outcomes among underserved populations. It is believed that the minimal risk involved in the proposed study is reasonable considering that it could lead to more effective ways to manage diabetes among vulnerable. Since participation in traditional diabetes self-management programs is low, delivering tailored problem-solving skills training could increase self-efficacy and adherence among *African Americans*, thus improving glycemic control and further reducing health complications.

G. Location where study will be performed: This study will take place at the University of Kansas School of Medicine-Wichita.

H. Collaboration (with another institution, if applicable): No collaboration with other institutions.

I. Single IRB Review for a Multi-site study (if applicable): N/A only single site IRB needed.

1. For which sites will KUMC serve as the IRB of record? All
2. Indicate which study activities will occur at each site. If all study procedures will be identical across study sites, state this. **KUMC Only Site**
3. Describe how you will assess the capacity of each site to perform the research (e.g., expertise, staffing, space, equipment, etc.) If applicable, include site evaluation tools in your IRB submission. **KUMC is the only site**

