7. Sustainability: No current plan. No partnership currently exist.

K. Personnel who will conduct the study, including:

1. Indicate, by title, who will be present during study procedure(s): [name], Study PI
2. Primary responsibility for the following activities, for example:
 - a. Determining eligibility: Research Assistant/ Principle Investigator
 - b. Obtaining informed consent: Research Assistant/ Principle Investigator
 - c. Providing on-going information to the study sponsor and the IRB: Research Assistant/ Principle Investigator
 - d. Maintaining participant's research records: Research Assistant/ Principle Investigator
 - e. Completing physical examination: Research Assistant/ Principle Investigator
 - f. Taking vital signs, height, weight: N/A
 - g. Drawing / collecting laboratory specimens: N/A- contracting out to a 3rd party
 - h. Performing / conducting tests, procedures, interventions, questionnaires: Research Assistant/ Principle Investigator
 - i. Completing study data forms: Research Assistant/ Principle Investigator
 - j. Managing study database: Research Assistant/ Principle Investigator

L. Assessment of Subject Safety and Development of a Data and Safety Monitoring Plan

1. Elements of the plan include:
 - a. Persons/groups who will review the data (study team; independent safety monitor, data monitoring committee or formal DSMB) Study team
 - b. Data/events that will be reviewed Timeline for data collection points, REDCap data entry process and logon's to eDECIDE website
 - c. Frequency of review: Will review daily/weekly and as needed to maintain study schedule
 - d. Types of analyses to be performed: Will run basic statistics or log entry to see how often participants log on to website. Will monitor computer security to ensure participant's confidentiality remains in take per HIPPA guidelines.
 - e. Safety-related triggers that would cause the PI to stop or alter the study Any breach in confidentiality based on the website

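### If participants are randomized one at a time, the fixed, printed block of 10 with open assignments and no described concealment lets recruiting staff foresee some allocations

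*Combined protocol and SAP*

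**What the plan says.** Section II.C gives the randomization rule in two sentences: "Block randomization with block size of 10 will be employed", and "Within each block 5 participants will be assigned at random to control and 5 to intervention group using computer derived labels". Both are repeated under Subject Enrollment (II.C, item 2). No other allocation procedure is described.

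The surrounding arrangements are:

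- **Blinding (II.C, item 1):** there is none, and "Participants and research staff will be aware of random group assignment".
- **Sites (II.I):** "KUMC is the only site". No stratification is mentioned, so there is one allocation sequence.
- **Roles (II.K.2):** "Determining eligibility: Research Assistant/ Principle Investigator"; "Obtaining informed consent: Research Assistant/ Principle Investigator"; "Managing study database: Research Assistant/ Principle Investigator".
- **Recruitment contact (II.D.1):** "The candidate will contact those who meet inclusion criteria to further undergo a telephone eligibility screen". Under III.C, study personnel telephone potential participants, go through the prescreen and then complete consent.
- **Database access (IV.A):** the investigator, research assistant and statistician can all open the REDCap database.

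The documents do not say who generates or holds the list, how the next assignment is hidden, or whether participants are assigned singly or in batches.

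**The concern.** Every block closes at exactly five and five, the block size is printed in the protocol, and staff see each assignment. Anyone who keeps a tally can therefore work out the end of each block, even if the list itself is hidden. The roles that could keep the tally are also the roles that screen and consent. Foreknowledge could affect how hard a candidate is encouraged, or when a consent call is made.

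The primary hypothesis (I.A) is that the two formats give comparable improvement. A difference in patient mix in either direction could therefore create or hide comparability. The planned regression adjusts for baseline HbA1c only, so selection on motivation or ease with computers would largely remain. No later analysis can fully repair it.

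**Working it through.** The plan states no figure for predictability, so there is none to reproduce.

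**Inputs.** Block size 10, so m = 5 places per arm (II.C); all past assignments known to staff (II.C, item 1); one sequence (II.I, no stratification described); 100 to be recruited with a goal of 70 (II.C). *Assumption:* participants are assigned one at a time, and each assignment is seen before the next person enters.

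**Step 1: allocations known with certainty.** Once one arm is full, every remaining place in the block is known. A given control place falls after all five intervention places with probability 1/(m+1), and the reverse holds equally. The expected number of certain places is therefore 2m/(m+1) = 10/6 = 1.67 per block, or 16.7%. That is about 16.7 of 100, or 11.7 of 70. At least the last place in every block is always known.

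**Step 2: best guess.** Always naming the arm with more places left gives expected correct guesses per block of m + 2^(2m−1)/C(2m, m) − 1/2 = 5 + 512/252 − 0.5 = 6.53 of 10, or 65.3%. A recursion over the places left gives the same value.

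**Step 3: alternative block sizes.** The fixed-size rows use the formulas above. The varying-size rows come from 1,500 simulated sequences of 100, with an observer who knows the set of sizes but not their order.

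| Scheme | Certain in advance | Best guess correct |
|---|---|---|
| Fixed 4 | 33.3% | 70.8% |
| Fixed 6 | 25.0% | 68.3% |
| Fixed 8 | 20.0% | 66.6% |
| **Fixed 10 (plan)** | **16.7%** | **65.3%** |
| Fixed 12 | 14.3% | 64.3% |
| Random 4/6/8 | about 2.4% | 67.9% |
| Random 8/10/12 | about 1.3% | 65.0% |

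Check on the last column: naming the arm with fewer assignments so far requires no knowledge of block sizes. Over complete blocks it gives (2.83 + 4.10 + 5.33)/18 = 68.1% for 4/6/8 and (5.33 + 6.53 + 7.72)/30 = 65.3% for 8/10/12. The simulated values are slightly lower because the last block is cut at 100.

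**Step 4: what this could do to HbA1c (illustration only).** The documents give no figure for unmeasured patient differences. *Assume* that favourable and unfavourable candidates, in equal supply, differ by 0.5 to 1.0 HbA1c points after baseline adjustment.

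- Steering every entry by best guess shifts the arm difference by (2 × 0.653 − 1) = 0.306 times the gap, or 0.15 to 0.31 points.
- Steering only on certain allocations shifts it by 0.167 times the gap, or 0.08 to 0.17 points.

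Section II.C treats a 0.5-point change as clinically meaningful. These are worst cases for deliberate steering, not forecasts.

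**The case against.** The best counter-argument concerns timing. The timeline in II.E.5 puts recruitment in June to August and enrollment from September. Sections II.B and II.E.2 place screening before randomization and mention group sessions. All of this is compatible with assigning batches after consent and baseline, in which case the foresight would disappear. This stands as far as making the figures conditional. It does not dispose of the point, because no batch step is stated either.

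It is also fair that 10 is a fairly large block, that about 83% of assignments are not certain, and that this is a pilot with a laboratory outcome adjusted for baseline. These limit the severity. A laboratory outcome protects measurement, however, not the choice of who enters which arm.

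A reader might infer more than the documents support:

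- **That one person screens patients and also delivers both arms.** Section II.B has the candidate leading the control sessions and the investigator as coach. But II.E.2 says a coach will be hired, and II.E.5 describes the control arm as self-directed on paper. That the candidate is the investigator is itself an inference.
- **That the suitability criterion gives recruiters discretion.** In II.D.1 that judgement belongs to clinicians, and nothing says they see or count assignments. Most of the other criteria are factual.
- **That bias is present.** Nothing shows that anyone has acted, or would act, on foreknowledge.

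**Conclusion.** The concern holds in conditional form. The stated rule itself permits foresight, beyond any gap in the description of concealment. It rests on three assumptions: one-at-a-time assignment, staff who know the printed block size, and staff who see all earlier assignments. The documents support the second and third and are silent on the first. On those terms about one allocation in six is known beforehand and about two in three can be guessed. This creates an opportunity for selection bias and does not demonstrate any. It should be corrected because the correction is cheap and can only be made prospectively.

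**What to change.** Replace the two randomization sentences, in both places where they appear, with a short procedure:

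1. The statistician generates permuted blocks of randomly varying size that are no smaller on average than now, for example 8, 10 and 12. Smaller sizes such as 4, 6 and 8 would also remove most certain predictions, but would raise the best-guess rate from about 65% to about 68%.
2. The block sizes are kept out of any document that recruiting staff see.
3. Only the statistician can open the allocation table. Releasing assignments through REDCap conceals nothing while the research assistant and investigator manage that database, so permissions must be restricted.
4. Each assignment is released only after eligibility, consent and baseline measures are recorded and locked. Alternatively, whole blocks are assigned together after that point.

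Varying the sizes removes nearly all certain predictions but leaves best guesses near 65%. Of these options, only whole-block assignment after locking removes the guessing as well, at the price of some participants waiting for their block to fill. The plan should state which is used.

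The other costs are a new computer-generated list, the restricted permissions, and a slightly larger possible arm imbalance if the last block is incomplete: at most 6 with a block of 12, against 5 with a block of 10 (and none at exactly 100 recruited). No extra participants are needed.

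Sections II.B, II.E.2 and II.E.5 should also be reconciled on who delivers each arm, so that a reader can tell who sees assignments.
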